3.2 Exclusion Criteria

- 3.21a Women of child-bearing potential, defined as all women physiologically capable of becoming pregnant, unless they are using highly effective methods of contraception during dosing and for 3 months after treatment completion.

Highly effective contraception methods include:

- Total abstinence (when this is in line with the preferred and usual lifestyle of the subject. NOTE: Periodic abstinence (e.g., calendar, ovulation, symptothermal, post-ovulation methods) and withdrawal are not acceptable methods of contraception)
- Female sterilization (have had surgical bilateral oophorectomy with or without hysterectomy) or tubal ligation at least six weeks before taking study treatment. In case of oophorectomy alone, only when the reproductive status of the woman has been confirmed by follow up hormone level assessment
- Male sterilization (at least 6 months prior to screening). NOTE: For female subjects on the study the vasectomized male partner should be the sole partner for that subject.
- Combination of any two of the following (a+b or a+c, or b+c):
 - a. Use of oral, injected or implanted hormonal methods of contraception or other forms of hormonal contraception that have comparable efficacy (failure rate <1%), for example hormone vaginal ring or transdermal hormone contraception.
 - b. Placement of an intrauterine device (IUD) or intrauterine system (IUS)
 - c. Barrier methods of contraception: Condom or Occlusive cap (diaphragm or cervical/vault caps) with spermicidal foam/gel/film/cream/vaginal suppository

NOTE:

- In case of use of oral contraception women should have been stable on the same pill for a minimum of 3 months before taking study treatment.
- Women are considered post-menopausal and not of child bearing potential if they have had 12 months of natural (spontaneous) amenorrhea with an appropriate clinical profile (e.g. age appropriate, history of vasomotor symptoms).

OR

- 3.21b Sexually active males unless they use a condom during intercourse while taking drug and for 5 months after stopping midostaurin medication.

NOTE:

- They should not father a child in this period.
- A condom is required to be used also by vasectomized men in order to prevent delivery of the drug via seminal fluid.

- 3.22 Co-morbid systemic illnesses or other severe concurrent disease which, in the judgment of the investigator, would make the patient inappropriate for entry into this study or interfere significantly with the proper assessment of safety and toxicity of the prescribed regimens.
- 3.23 Immunocompromised patients (other than that related to the use of corticosteroids) including patients confirmed to be HIV positive or have active viral hepatitis.
- 3.24 Uncontrolled intercurrent illness including, but not limited to, ongoing or active infection, or psychiatric illness/social situations that would limit compliance with study requirements. Patients with any other known concurrent severe and/or uncontrolled medical condition (except carcinoma in-situ), which could compromise participation in the study (e.g. uncontrolled infection, uncontrolled diabetes, chronic active pancreatitis) .
- 3.25 Receiving any other investigational agent which would be considered as a treatment for the primary neoplasm.
- 3.26 Other active malignancy ≤ 1 year prior to registration. EXCEPTIONS: Non-melanotic skin cancer or carcinoma-in-situ of the cervix.
- 3.27 Previous treatment with specific chemotherapy (cytarabine, idarubicin, daunorubicin) or hypomethylating drug (decitabine or azacitidine) for a hematological disorder. EXCEPTIONS: Prior hydroxyurea allowed. Secondary AML is allowed.
- 3.28 Impaired cardiac function including any of the following:
- Inability to monitor the QT interval on ECG
 - Congenital long QT syndrome or a known family history of long QT syndrome.
 - Clinically significant resting brachycardia (< 50 beats per minute)
 - QTc > 450 msec on baseline ECG. NOTE: If the ECG shows a QTc interval greater than 450 msecs at screening triplicates should be performed, one minute apart to confirm the finding (after replacement of any electrolyte imbalance). If 2/3 or 3/3 of the ECGs confirm the QT prolongation (i.e. QTc interval > 450 msecs) the patient must not be included into the trial.
 - Myocardial infarction ≤ 3 months prior to starting study
 - Other clinically significant uncontrolled heart disease (e.g. unstable angina, congestive heart failure or uncontrolled hypertension)
 - History of or presence of clinically significant ventricular, atrial tachyarrhythmias or ejection fraction cutoff
 - Left ventricle ejection fraction $< 45\%$
 - History of Congestive heart failure requiring use of ongoing maintenance therapy for life-threatening ventricular arrhythmias.
- 3.29a Patients currently receiving treatment with strong CYP3A4 inhibitors

and treatment that cannot be either discontinued or switched to a different medication prior to starting study drug. Patients receiving any medications or substances that are strong inhibitors of CYP3A4. All Azoles but fluconazole are discouraged to be used in patients requiring treatment with antifungal antibiotics.

Use of the following strong inhibitors is prohibited ≤ 7 days prior to registration.

Strong Inhibitors of CYP3A4/5 > 5-fold increase in the plasma AUC values or more than 80% decrease in clearance
Boceprevir (Victrelis®) Clarithromycin (Biaxin®, Biaxin XL®) Conivaptan (Vaprisol®) Indinavir (Crixivan®) Itraconazole (Sporanox®) Ketoconazole (Nizoral®) Lopinavir/Ritonavir (Kaletra®) Mibefradil Nefazodone (Serzone®) Nelfinavir (Viracept®) Posaconazole (Noxafil®) Ritonavir (Novir®, Kaletra®) Saquinavir (Fortovase®, Invirase®) Telaprevir (Incivek®) Telithromycin (Ketek®) Voriconazole (Vfend®) troleandomycin cobicistat tipranavir

3.29b Receiving any medications or substances that are **inducers** of CYP3A4. Use of the following inducers are prohibited ≤ 7 days prior to registration.

Strong Inducers of CYP3A4/5 > 80% decrease in AUC
Avasimibe Carbamazepine (Carbatrol®, Eptol®, Equetro™, Tegretol®, Tegretol-XR®) Phenytoin (Dilantin®, Phenytek®) Rifampin (Rifadin®) St. John's wort mitotane rifabutin phenobarbital
Moderate Inducers of CYP3A4/5 50-80% decrease in AUC
Bosentan (Tracleer®) Efavirenz (Sustiva®)

Etravirine (Intelence®) Modafinil (Provigil®) Nafcillin Genistein Ritonavir Talyraline Thioridazine Tipranavir Nevirapine (Viramune®) Phenobarbital (Luminal®) Rifabutin (Mycobutin®) Troglitazone

- 3.29c Patients currently receiving treatment with any medications that have the potential to prolong the QT interval and the treatment cannot be either discontinued or switched to a different medication prior to starting study drug. NOTE: Prohibited medications are listed in Appendix Ia “Drugs With Risk of Torsades de Pointes.” Appendix Ib contains drugs that should be used with caution due to possible or conditional risk of Torsades de Pointes.
- 3.29d Impaired gastrointestinal (GI) function or GI disease that may significantly alter the absorption of study drug (e.g., ulcerative diseases, uncontrolled nausea, vomiting, diarrhea, malabsorption syndrome, small bowel resection or gastric bypass surgery).
- 3.29e Acute or chronic pancreatic disease.
- 3.29f Known cytopathologically confirmed CNS infiltration.
- 3.29g Acute or chronic liver disease or severe renal disease considered unrelated to the cancer.
- 3.29h History of significant congenital or acquired bleeding disorder unrelated to cancer.
- 3.29i Major surgery ≤ 4 weeks prior to registration of the study or who have not recovered from prior surgery regardless of time since surgery.
- 3.29j Treatment with other investigational agents ≤ 30 days or 5 half - lives of registration.
- 3.29k Diagnosis of AML-M3 (or acute promyelocytic leukemia).

4.0 Test Schedule

All routine assessments must be performed within ± 7 days of the day indicated on the Visit Schedule.

Tests and procedures	Pre-Treatment	Active Treatment					
	≤ 7 days prior to registration*	Cycle 1, Day 1	Cycle 1, Day 8	Cycle 1 Day 21	Cycles 2 and above, Day 1	Cycles 2 and above, Day 8 ⁷	Early Discontinuation or End of Treatment
History and exam, weight, vitals, PS	X	X			X	X	X
Height	X						
Adverse event assessment	X	X			X		X
BM testing ²	X				X ²		X
Biomarkers FLT3 Mutation by PCR	X						X
Pregnancy Test	X						
Hematology group(CBC) Hgb, , PLT, WBC with diff. ¹	X	X ¹	X	X	X ¹	X	X
Serum Chemistry (magnesium, potassium, phosphorus, total bilirubin, direct bilirubin ⁵ , alkaline phosphatase, AST, ALT, creatinine)	X	X	X	X	X	X	X
Serum Chemistry (Serum Amylase & Lipase)	X	X			X		X
MUGA/Echo	X						
LDH	X						
Urine analysis (proteinuria, hematuria) ^R	X						
ECG (QTcF results preferred) ^{R 3}	X		X			X ³	X
Patient Medication Diary (Appendix III ⁴)			X		X	X	
Research Correlatives ^{R, 6}	X		X		X ⁶		

* Labs done on the same day of consent but prior to consenting do not need to be repeated.

1. CBC will be done weekly for cycle 1-4. After cycle 4, to be performed Day 1 and Day 8.
2. Bone marrow (BM) sampling will be done upon screening, and day 1 of cycle 3, 5, 9 and then as clinically needed. Recent bone marrow within 21 days (even prior to consenting) will be acceptable and FLT3 PCR could be done on peripheral blood if blasts >10%. Outside FLT3

testing at bone marrow biopsy will be allowed and used if done.

3. ECGs will be performed locally at screening, Day 8 (prior to dosing) of each cycle, and when there's any dose change due to QTc prolongation or re-initiation after a dose interruption. When a dose change occurs due to QTc prolongation or upon re-starting midostaurin, an ECG must be obtained at 7 days afterwards. QTcF results are preferred, however all reporting methods will be accepted.
 4. The diary must begin the day the patient starts taking midostaurin and must be completed per protocol and returned to the treating institution OR compliance must be documented in the medical record by any member of the care team. Patients will be asked to return all unused medication at each visit.
 5. Get direct bilirubin if total bilirubin > upper normal limit.
 6. Correlatives for blood and bone marrow. See section 14.
 7. If midostaurin is started on day 1, then do these tests on day 1. If midostaurin is started on day 8, then do these tests on day 8.
- R Research funded (see Section 19.0). This will be charged to study and not to patient's account.

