Overall, approximately 1687 subjects have received midostaurin including ~650 patients with AML / MDS. In AML patients, doses of up to 600 mg per day have been given, but the 50 mg twice daily dose is recommended based upon reaching the IC50 and showing acceptable tolerability. Safety data in AML are based upon three studies: monotherapy in FLT3 mutated patients (2104 Core; N=20), monotherapy in relapsed AML or ineligible for chemotherapy (2104E1; N=95) and front-line combination therapy with daunorubicin and cytarabine (2106; N=69). (Stone 2005, Fischer 2010, Stone 2012). Data from the maintenance phase of the Phase III (2301, CALGB 10603 Ratify) study would also be very informative but the ongoing trial remains blinded at this time. Single agent safety data from 2104E1 will be discussed.

In study 2104E1, patients were randomized to receive midostaurin at doses of 50 mg b.i.d. or 100 mg b.i.d. Of the patients enrolled, 73% were relapsed/refractory and 61% were greater than 60 years of age. Six patients had previously undergone HSCT. Midostaurin was generally well tolerated at both dose levels. All 95 patients experienced at least one AE regardless of relationship to study drug. The most frequent events were grades 1 or 2 nausea (61%; Grade 3 was 1%), vomiting (49%; Grade 3 was 1%), diarrhea (44%; Grade 3 or 4 was 5%), fatigue (38%; Grade 3 was 3%), pyrexia (35%; Grade 3 was 7%) and dyspnea (29%; Grade 3 or 4 9%). The most commonly reported grade 3 / 4 AEs were febrile neutropenia (21%), thrombocytopenia (19%), neutropenia (12%), anemia (13%) and pneumonia (12%). [Inv Brochure ed 16, Table 6-20] The decreases observed in the hematology parameters were as expected for this patient population. Only one patient discontinued treatment due to a hematologic

abnormality (grade 3 febrile neutropenia). The majority of new or worsened biochemistry abnormalities were of CTC grade 1-2. There were grade 3 or 4 abnormalities in AST/ALT in 13% patients (2 were Grade 4, both receiving 100 mg b.i.d.), amylase 7% and albumin 5%. The full table of newly occurring or worsening hematology and chemistry abnormalities is shown in the Investigators Brochure.

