7.0 Protocol Treatment

7.1 Treatment Schedule

- 7.11 Patients eligible for the study based on screening tests will be enrolled on the study.
- Patients will proceed to next cycle every 28 days (or later) based on investigator opinion when reviewing each case based on hematological and physical findings.
 - Patients who tolerate combination therapy well and fail to achieve CR/CRi/PR/morphologic leukemia-free state by end of cycle 2, could get midostaurin on days 1-28 of each subsequent cycle, rather than just days 8-21, as per treating MD decision.
 - Patients who achieve a CR/CRi/PR/morphologic leukemia-free state by end of cycle 8 will continue on current regimen.
 - Patients who fail to achieve a CR/CRi/PR/ morphologic leukemia-free state in bone marrow blasts by end of cycle 8 will go to event monitoring.
 - Patients will get a repeat bone marrow biopsy on day one of cycles 3, 5, 9 and then as clinically indicated (see Test Schedule, section 4.0). Patients who achieve CR/CRi will not need repeat bone marrow assessment unless deemed necessary by investigator.
 - Hydroxyurea and/or leukocytapheresis use is allowed to control rising blasts as deemed necessary by treating investigator at any

time.

Cycle length = 28 days (+/- 7 days)

Agent	Dose	Route	Day	Comments
Decitabine ¹	20 mg/m ²	IV	1-5	Could be given days 2-5 by local MD (outside Mayo Clinic).
Midostaurin ²	50 mg twice/day	Oral	8-21	Midostaurin could be given continuously (day 1-28) starting cycle 3 based on MD decision (see 7.11).

1. May be held as per treating physician judgment.
2. If decitabine is held, then midostaurin will be held. If decitabine is administered, midostaurin cannot be held, but can be omitted.

7.12 Maximum cycles of midostaurin are 18, after which a discussion with Novartis will be done on a per patient basis whether to keep patient on continued therapy with the combination of decitabine and midostaurin on study (continue active monitoring per section 4.0).

7.13 If midostaurin is discontinued, single agent Decitabine may be given beyond cycle 18 off protocol until relapse or disease progression off protocol. The patient will go to event monitoring per section 18.0

Note: If single agent Decitabine is being given off protocol, the end of active treatment form should be filled out at the end of cycle 18. Reason treatment ended should be reported as treatment completed per protocol criteria.

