8.2 Midostaurin dose adjustments for AE at least possibly related to treatment

→ → Use the NCI Common Terminology Criteria for Adverse Events (CTCAE) version 4.0 unless otherwise specified ← ←			
CTCAE System/Organ/Class (SOC)	ADVERSE EVENT	AGENT	ACTION
AT TIME OF NEXT DOSE (All treatment days of each cycle)			
Blood and lymphatic system disorders	Grade 4 Febrile Neutropenia	Midostaurin ¹	
1st event: First event days 2-28, omit midostaurin dose until recovery then restart at 50mg b.i.d
 
2nd event: Omit midostaurin until recovery then restart at 25mg b.i.d for 2 weeks and then re-escalate to 50mg b.i.d as tolerated.
 
3rd event: Third event, patient should be discontinued if neutropenia is attributable to midostaurin

			
If alternate causes of liver dysfunction have been managed, but liver dysfunction persists, Omit midostaurin until recovery to Grade 2 then restart.
 
If this is felt to be related to study drug and the re-challenge results in a subsequent Grade 3 or 4 elevation, then patient should be discontinued from treatment.

Investigations	Grade 3 or 4 increased Bilirubin, AST, or ALT		
Gastrointestinal Disorders	Grade 2 Nausea or Vomiting	Midostaurin ¹	If this develops despite use of standard anti-emetic therapy and persists for at least 3 days, Omit midostaurin for 3 days (6 doses) and resume midostaurin as tolerated.
	Grade 3 or 4 Nausea or Vomiting		If this develops and persists despite use of standard anti-emetic therapy, omit midostaurin until recovery to Grade 2 (or at least 3 days) then restart. If this is felt to be related to study drug and the re-challenge results in a subsequent Grade 3 or 4 toxicity then the patient should be discontinued from treatment.

→ → Use the NCI Common Terminology Criteria for Adverse Events (CTCAE) version 4.0 unless otherwise specified ← ←			
CTCAE System/Organ/Class (SOC)	ADVERSE EVENT	AGENT	ACTION
Gastrointestinal Disorders	Grade 3 or 4 Diarrhea		If this develops and persists despite use of standard anti-diarrheal therapy(see section 9.4), omit midostaurin until recovery to Grade 2 (or at least 3 days) then restart.
Respiratory, thoracic and mediastinal disorders	Grade 3 or 4 Pneumonitis		Omit midostaurin until recovery to ≤ Grade 1 and then resume dosing.

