Caution should be exercised for patients receiving moderate CYP3A4 inhibitors. A list of these agents is found at:

<http://medicine.iupui.edu/clinpharm/ddis/main-table>

Co-administration of midostaurin with the potent CYP3A4 inducer, rifampicin, decreased the C_{max} and AUC of midostaurin by 73% and 94%, respectively. To avoid sub-therapeutic exposure to midostaurin, moderate or strong CYP3A4 inducers should not be co-administered. Strong CYP3A4 inducers include: avasimibe, carbamazepine, mitotane, phenobarbital, phenytoin, rifabutin, rifampin (rifampicin), and St. John's wort. Moderate CYP3A4 inducers include: bosentan, efavirenz, etravirine, genistein, modafinil, nafcillin, ritonavir, talviraline, thioridazine, and tipranavir.

- 15.17 **Known potential toxicities:** Aggressive Systemic Mastocytosis (ASM), and Acute Myeloid Leukemia (AML)

Very Common (>10%): leukopenia, lymphopenia, febrile neutropenia (AML), petechiae, sinus tachycardia, anorectal discomfort, constipation, diarrhea, hemorrhoids, stomatitis, nausea, vomiting, fatigue, peripheral edema, pyrexia, hypersensitivity (AML), device related infection, URTI (ASM), UTI, APTT prolonged, increased ALT, increased AST, increased amylase, increased lipase, decreased hemoglobin, decreased neutrophil count, decreased absolute neutrophils, decreased absolute lymphocytes, hyperglycemia, increased glucose, hypokalemia, hyponatremia, increased total bilirubin, hyperuricemia, back pain, arthralgia, headache, dizziness, insomnia, cough, dyspnea, epistaxis, pleural effusion (ASM), laryngeal pain, hyperhidrosis, exfoliative dermatitis, hypertension,

hypotension (AML)

Common (> 1- 10%): febrile neutropenia (ASM), pericardial effusion, eyelid edema, vertigo, abdominal discomfort, abdominal distension, dyspepsia, GI hemorrhage, asthenia, chills, edema, catheter related thrombosis, hypersensitivity (ASM), bronchitis, erysipelas, cystitis, herpes zoster, oral herpes, pneumonia, sepsis, sinusitis, URTI (AML), hypercalcemia, increased weight, confusion, fall, bone pain, pain in extremities, neck pain, syncope, tremor, disturbance in attention, ARDS, pleural effusion (AML), oropharyngeal pain, nasopharyngitis, keratitis, dry skin, hematoma, hypotension (ASM)

Uncommon ($\geq 0.1 - 1\%$): anaphylactic shock, neutropenic sepsis

- 15.18 **Drug procurement:** Midostaurin capsules will be provided free of charge to study subjects by Novartis.
- 15.19 Nursing Guidelines

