Accrual will be temporarily suspended to this study if at any time we observe events considered at least possibly related to study treatment (i.e. an adverse event with attribute specified as "possible," "probable," or "definite") that satisfy one of the following:

- if 4 or more patients in the first 12 treated patients experience a grade 4 or higher non-hematologic adverse event at least possibly related to treatment excluding infections and hypophosphatemia, hypocalcemia, hypo- or hyperkalemia, hyperuricemia as these abnormal lab results tend to resolve quickly (≤ 7 days) without affecting or jeopardizing patient safety.
- if after the first 12 patients have been treated, 30% of all patients experience a grade 4 or higher non-hematologic adverse event at least possibly related to treatment excluding infections and hypophosphatemia, hypocalcemia, hypo- or hyperkalemia,

hyperuricemia as these abnormal lab results tend to resolve quickly (≤ 7 days) without affecting or jeopardizing patient safety.

We note that we will review grade 4 and 5 adverse events deemed “unrelated” or “unlikely to be related”, to verify their attribution and to monitor the emergence of a previously unrecognized treatment-related adverse event.

16.5 Results Reporting on ClinicalTrials.gov: At study activation, this study will have been registered within the “ClinicalTrials.gov” website. The Primary and Secondary Endpoints along with other required information for this study will be reported on ClinicalTrials.gov. For purposes of timing of the Results Reporting, the initial estimated completion date for the Primary Endpoint of this study is 2.5 years after the study opens to accrual. The definition of “Primary Endpoint Completion Date” (PECD) for this study is at the time the last patient registered has been followed for at least 6 months.

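### On default day 8-21 dosing, no nominal amylase/lipase draw after midostaurin begins falls on a dosing day, and no liver test is timed to a re-start after a Grade 3-4 liver omission

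*Combined protocol and SAP*

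**What the plan says.** **Enzymes.** The Section 4.0 row "Serum Chemistry (Serum Amylase & Lipase)" is marked at screening, Cycle 1 Day 1, Day 1 of cycles 2 and above, and end of treatment. It is blank at Cycle 1 Day 8, Cycle 1 Day 21 and Day 8 of later cycles. Section 7.1 gives midostaurin on days 8-21 of a 28-day cycle. The one variant is for patients without a response by the end of cycle 2: "Midostaurin could be given continuously (day 1-28) starting cycle 3 based on MD decision".

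Section 15.17 lists "increased ALT, increased AST, increased amylase, increased lipase" among the very common toxicities (over 10%). In the monotherapy study, with 50 and 100 mg b.i.d. pooled, Section 1.2 reports "grade 3 or 4 abnormalities in AST/ALT in 13% patients (2 were Grade 4, both receiving 100 mg b.i.d.), amylase 7" per cent.

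Under the last row of Section 8.2, midostaurin is held for other related Grade 3 non-hematologic toxicity and discontinued for Grade 4. Section 16.325 tabulates each patient's maximum grade. Section 16.42 suspends accrual "if 4 or more patients in the first 12 treated patients experience a grade 4 or higher non-hematologic adverse event". Only events with a possible or stronger link to the regimen count, and the rule exempts infections and a short list of electrolyte and uric acid results. Amylase and lipase are not among those exclusions.

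**Liver.** Bilirubin, AST and ALT are marked in every column of Section 4.0, including Cycle 1 Day 21 and Day 8 of later cycles. For a persistent Grade 3-4 elevation Section 8.2 says: "Omit midostaurin until recovery to Grade 2 then restart". If the drug is thought responsible and "the re-challenge results in a subsequent Grade 3 or 4 elevation", the patient comes off treatment. Footnote 3 of Section 4.0 requires an ECG 7 days after midostaurin is re-started. It asks for no liver test then. Footnote 7 moves the Day 8 tests to Day 1 when midostaurin starts on Day 1.

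**The concern.** The plan treats pancreatic enzymes as a known midostaurin effect. Section 3.15 sets an entry limit on them, and Section 10.51 names lipase for grading at each evaluation. Yet on the default schedule they are measured only after each two-week block has been over for about a week. A rise that appears during dosing and has settled by the next Day 1 need never be seen. It would then trigger no hold or discontinuation and would be absent from the adverse event table. Any resulting bias is toward understating toxicity of this combination.

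The liver point is separate. Section 8.2 turns on the result of a re-challenge, but no test is timed to read that result. From cycle 2 a failed re-challenge need not be seen until the rest of the block has been taken.

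**Working it through.** The plan states no figure on this point, so there is none to reproduce. The check is a calendar count on nominal days with 28-day cycles.

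**1. Enzyme draws against dosing days**
- There is one Day 1 draw per cycle: 8 over 8 cycles, 18 over 18 cycles.
- Cycle 1 Day 1 precedes any midostaurin and is left out: 8 - 1 = 7 and 18 - 1 = 17.
- Dosing days over 18 cycles: 18 x 14 = 252. Draws on a dosing day: 0 of 7 and 0 of 17.
- Last dose on the evening of Day 21 to the morning of Day 29: 7.5 days.
- Window: Day 1 ±7 days runs from the prior Day 22 to Day 8. Only the +7 limit reaches a dosing day, and that is the first one.
- Continuous dosing starts at cycle 3 at the earliest, so the first nominal draw that follows doses within a continuous block is Cycle 4 Day 1, study day 1 + 3 x 28 = 85.

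**2. How far off drug is Day 1?** Half-lives are from Sections 1.2 and 15.15; 7.5 days = 180 hours.
- Midostaurin, 17-25 h: 0.5^(180/17) = 0.0006 to 0.5^(180/25) = 0.007, so under 1% remains.
- CGP62221, 30-39 h: 0.5^(180/30) = 0.016 to 0.5^(180/39) = 0.041, so about 2-4%.
- CGP52421, about 28 days: 0.5^(7.5/28) = 0.83, so about 83%.

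**3. How many patients might have an event?** Assume the 7% Grade 3-4 amylase rate from monotherapy, or half of it, applies here.
- Expected among 26 patients: 26 x 0.035 = 0.9 to 26 x 0.07 = 1.8.
- Chance of at least one: 1 - 0.965^26 = 0.60 to 1 - 0.93^26 = 0.85.
- These are chances that an event occurs, not that one is missed. The documents give no enzyme recovery time, so the missed share cannot be computed.

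**4. Stopping rule.** Suppose every one of these events were Grade 4 and related. Amylase alone would reach 4 of 12 with binomial probability 0.0075 at 7%, or 0.0006 at 3.5%.

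**5. Re-start to next scheduled liver draw**

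| Situation | Re-start day | Next draw | Interval |
|---|---|---|---|
| Cycle 1, days 8-21 | 8 to 20 | Cycle 1 Day 21 | 13 down to 1 days |
| Cycle 1, days 8-21 | 21 | Cycle 2 Day 1 | 8 days |
| Cycle 2 on, days 8-21 | 8 to 21 | next Day 1 | 21 down to 8 days |
| Days 1-28 dosing | 1 to 28 | next Day 1 | 28 down to 1 days |

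- Day 8 re-start from cycle 2: 14 days x 2 = 28 doses before the next draw. A test on Day 15 acted on that day could spare Days 15-21, 7 x 2 = 14 doses.
- Day 1 re-start on continuous dosing: 28 x 2 = 56 doses. A test on Day 8 could spare Days 8-28, 21 x 2 = 42 doses.

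**The case against.** Several counter-arguments stand and limit the point.

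- **Harm from the enzyme gap is not demonstrated.** It needs a Grade 3-4 rise that resolves within about 7.5 days of the last dose. The documents do not say how often that happens, and one active metabolite is still largely present on Day 1. The end-of-treatment column also prompts a draw if a patient stops mid-block, and investigators may order unscheduled tests.
- **The liver exposure is bounded.** On days 8-21 dosing the next Day 1 panel comes before the next block opens, so at most the rest of one block is at stake. The 8.2 liver row acts on dysfunction that persists, so nothing is claimed here about transient liver rises. The 56-dose case needs a patient without response moved to continuous dosing who also had a liver omission and re-started on Day 1.
- **The ECG comparison is imperfect.** Section 8.2 justifies extra QTc care by saying the effect is not fully characterized. It says nothing similar about the liver.

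Four stronger readings are tempting, and the documents do not support them. A reader might infer that no liver test follows a re-start at all, but the liver row is marked in every column. A reader might see a conflict with Section 10.51, but amylase and lipase are drawn at every scheduled adverse event assessment. A reader might take 60-85% as the chance of missing an event, but it is the chance that one occurs. Finally, a reader might conclude that the stopping rule is compromised. Step 4 shows a negligible effect even on extreme assumptions.

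**Conclusion.** The point holds as a minor gap in safety monitoring. After midostaurin begins, no nominal enzyme draw on the default schedule falls on a dosing day, and for cycles 1 and 2 this applies to every patient. A rise confined to the interval between draws has no required test. Any bias understates enzyme toxicity, by an amount the documents do not allow to be estimated. For the liver, what is missing is a test timed to the re-start. From cycle 2 on days 8-21 dosing the next one falls after the block has ended.

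This rests on nominal visit days, 28-day cycles and, for the event counts, carrying the pooled monotherapy amylase rate over to this combination. The CR/CRi primary endpoint and its decision rule are unaffected.

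**What to change.** Make two edits to Section 4.0.

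1. Mark amylase and lipase at the existing Cycle 1 Day 21 chemistry draw. Require that sample while midostaurin is still being taken, with a window of Day 14 to Day 21. The general ±7 days would allow Days 14-28, and Days 22-28 are off dosing.
2. Add to footnote 3 that after a Grade 3-4 liver omission, bilirubin, AST and ALT are repeated at the ECG already required 7 days after re-start.

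Later default-schedule cycles would still have no on-dosing enzyme sample, so the report should say that those rates come from samples taken off dosing days.

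**Cost.** One added enzyme occasion per patient, about 26 in all, at an existing draw. Liver panels number about 1-3 in total: 26 x 0.05 = 1.3 to 26 x 0.13 = 3.4, assuming 5-13% of patients have a Grade 3-4 elevation and re-start once. The 13% is the monotherapy AST/ALT rate; the 5% is an assumption. No new visit is needed. The weekly CBC of cycles 1-4 can carry the liver sample, while after cycle 4 it may need a venipuncture at the ECG visit. Chemistry is not marked as research funded, so the payer must be settled under Section 19.1.
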